## **8.2 Clinical and Safety Assessments**

### **8.2.1 Adverse Events (AEs) and Serious Adverse Events (SAEs)**

At each visit the study navigator assesses for AEs and SAEs by asking the study participant, "How have you been feeling since your last visit?" AEs and SAEs may also be spontaneously reported to study staff at any visit following consent. AEs and SAEs suggesting medical or psychiatric deterioration will be brought to the attention of a study clinician for further evaluation and management. Visits will emphasize overdose risk and risk-management. Any reported overdose is recorded as an AE or SAE, or in a separate form. AE and SAE reporting is according to the reporting definitions and procedures outlined in the protocol and in accordance with applicable regulatory requirements.

For the purpose of this study, the following AEs do not require reporting in the data system but is captured in the source documentation as medically indicated:

Grade 1 (mild) unrelated adverse events. This would typically include mild physical events such as headache, cold, etc., that were considered not reasonably associated with the study intervention.

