### **11.13.1 Adverse Events (AEs)**

Specific adverse events that will be collected in this study are described in further detail in Appendix A.

Two study clinicians are have been appointed in this project, who will review or provide consultation for each Serious Adverse Event (SAE) as needed at each site. These reviews will include an assessment of the possible relatedness of the event to the study intervention or other study procedures. Study clinicians will also provide advice for decisions to exclude, refer, or withdraw participants as required.

Each of the sites has established practices for managing medical and psychiatric emergencies, and the study staff will continue to utilize these procedures. Treatment providers at each site will

be responsible for monitoring participants for possible clinical deterioration or other problems, and for implementing appropriate courses of action.

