## 14.0 APPENDIX A: ADVERSE EVENT REPORTING AND PROCEDURES

Each participating site's Principal Investigator is responsible for study oversight, including ensuring human research subject protection by designating appropriately qualified and trained study personnel to assess, report, and monitor adverse events. See AE form in the electronic data capture program.

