### Definition of Adverse Events and Serious Adverse Events

An **adverse event** (AE) is any unexpected medical occurrence in humans, whether or not considered study intervention related which occurs during the conduct of a clinical trial. Changes from baseline in clinical status; i.e., death, miscarriage, pre-term birth, overdose, relapse, child protective services involvement including child removal; that are considered clinically significant by the study medical clinician are considered AEs.

**Suspected adverse reaction** is any adverse event for which there is a reasonable possibility that the study intervention caused the adverse event. A reasonable possibility implies that there is evidence that the study intervention caused the event.

**Adverse reaction** is any adverse event caused by the study intervention.

An **adverse event, suspected adverse reaction, or adverse reaction** is considered "**serious**" (i.e., a serious adverse event, serious suspected adverse reaction or serious adverse reaction) if, in the view of either the study medical clinician or sponsor, it:

- 1) Results in death: A death occurring during the study or which comes to the attention of the study staff during the protocol-defined follow-up period, whether or not considered caused by the study intervention, must be reported.
- 2) Is life-threatening: Life-threatening means that the study participant was, in the opinion of the medical clinician or sponsor, at immediate risk of death from the reaction as it occurred and required immediate intervention.
- 3) Requires inpatient hospitalization or prolongation of existing hospitalization.
- 4) Results in persistent or significant incapacity or substantial disruption of the ability to conduct normal life functions.
- 5) Is a congenital abnormality or birth defect.
- 6) Is an important medical event that may not result in one of the above outcomes, but may jeopardize the health of the study participant or require medical or surgical intervention to prevent one of the outcomes listed in the above definition of serious event.

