## **Site's Role in Eliciting and Reporting Adverse Events**

Appropriately qualified and trained personnel will elicit participant reporting of AEs and SAEs at each study visit designated to collect AEs. Adverse events (medical and/or psychiatric) assessment will initiate with participant consent and follow-up will continue through the final assessment. Study personnel will obtain as much information as possible about the reported AE/SAE to complete the AE/SAE forms and will consult as warranted.

Standard reporting, within 7 days of the site becoming aware of the event, is required for reportable AEs. Expedited reporting (within 24 hours of their occurrence and/or site's knowledge of the event) is required for reportable SAEs (including death and life-threatening events). Local sites are responsible for reporting SAEs to the IRB of record, per the IRB or record's guidelines.

Sites are required to enter reportable AEs and SAEs in data capture program. The AE form is used to capture reportable AEs and SAEs (as defined in the protocol) and will be reviewed by the study PI upon submission. Additional information may need to be gathered to evaluate SAEs and to complete the appropriate CRFs and the summary. This process may include obtaining hospital discharge reports, medical records, autopsy records or any other type records or information necessary to provide a complete and clear picture of the serious event and events preceding and following the event. If the SAE is not resolved or stable at the time of the initial report or if new information becomes available after the initial report, follow-up information must be submitted as soon as possible.

Reportable adverse events will be followed until resolution, stabilization or study end. Any serious adverse reactions will be followed until resolution or stabilization even beyond the end of the study.

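### The one scripted adverse-event question asks how the mother has been feeling, and no structured prompt or scheduled record check shown identifies custody events or birth defects as adverse events

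*Combined protocol and SAP*

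**What the plan says.** Section 8.2.1 sets the method: "At each visit the study navigator assesses for AEs and SAEs by asking the study participant" a single open question, "How have you been feeling since your last visit". It then adds that "AEs and SAEs may also be spontaneously reported to study staff at any visit following consent". The same section has visits stress overdose risk and has reported overdoses recorded.

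Appendix A, under its definitions, lists changes in clinical status that count as adverse events once the study medical clinician judges them clinically significant: "death, miscarriage, pre-term birth, overdose, relapse, child protective services involvement including child removal". One of its seriousness criteria reads "Is a congenital abnormality or birth defect". Section 11.13.1 commits to capture: "Specific adverse events that will be collected in this study are described in further detail in Appendix A".

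On how events are found, Appendix A says "Appropriately qualified and trained personnel will elicit participant reporting of AEs and SAEs at each study visit designated to collect AEs". For the form it says only "See AE form in the electronic data capture program", and the form's fields are not reproduced.

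The assessment table in section 8.0, which presents itself as exhaustive, has no row named for child protective services, child removal, birth defects or gestational age at delivery. Its infant rows are neonatal abstinence syndrome (NAS) and pediatric visits, both from medical records.

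**The concern.** The question and its target do not match. Appendix A names occurrences, and several concern the infant or custody. A mother can answer a question about how she has been feeling truthfully and fully without mentioning a child protective services contact or a malformation found in the newborn. For custody events she may also have a reason to stay silent: section 12.0, part F, says the consent form will tell her that suspected child abuse is reportable.

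What is at stake is the use made of the adverse-event data. Section 12.0, part C, uses them with clinical outcomes to judge whether the benefit-to-risk balance has shifted and whether the study should continue, change or stop. The DSMB receives adverse-event listings and SAE summaries. If the protocol's own named harms are captured patchily, both reviews work from a thin record. If the chance of capture also depends on the arm, the record is uneven as well as thin.

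**Working it through.** The plan states no figure on this point, so there is none to reproduce. The check compares each named event with whatever in the documents would bring it to light, and then compares the arms' occasions for disclosure.

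**Step 1. Event by event**

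- *Death, miscarriage.* Both end follow-up under section 7.6, and the study completion form (8.1.4) tracks status. The study has to learn of them.
- *Relapse.* Timeline Follow Back and urine toxicology are scheduled at all four assessments (8.0). Covered.
- *Overdose.* Section 8.2.1 has visits raise the topic and reported overdoses recorded. Partly covered.
- *Pre-term birth.* Gestational age is confirmed by ultrasound at entry (5.1), and two assessments are timed from delivery (7.8). Staff could derive it, but no step tells them to do so or to enter it as an adverse event.
- *Child protective services involvement, child removal.* No row in 8.0 is named for them. Social service visits come from agency records, but the documents do not say whether child protective services is among those agencies. No scheduled check is given.
- *Birth defect.* No row in 8.0 is named for it. NAS and pediatric visits are taken from records as outcomes, and nothing routes those records into adverse-event reporting.

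So custody events and birth defects have no dedicated source, and pre-term birth has usable data without a stated step.

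**Step 2. Could another provision fill the gap?**

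- Section 7.2 obtains access to site medical records and community agency records. This is permission, not a scheduled review.
- Appendix A has records gathered to evaluate an SAE. That follows up events already known.
- The monthly safety review topics in section 12.0, part C, do not include these events, although that list is stated to be non-exhaustive.

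**Step 3. Occasions for disclosure by arm**

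- Navigation arm: up to 10 prenatal plus 4 postnatal sessions (3.2, 7.5) = up to 14, each 1 to 1.5 hours. 14 × 1 = 14 hours; 14 × 1.5 = 21 hours at most.
- Both arms: three assessments after baseline, 30 to 45 minutes each (7.8). 3 × 30 = 90 minutes; 3 × 45 = 135 minutes.
- Standard care adds brief case management and referral (7.5), with no duration given.

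Navigation sessions cover family services and newborn care. Section 8.2.1 also gives the open question to the navigator, who delivers the navigation intervention under 7.5. The documents do not say who puts it to standard-care women, while Appendix A assigns elicitation to trained personnel generally. These figures show unequal opportunity. They do not measure how many events each route would find.

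**The case against.** The strongest reply is that the protocol does more than ask one question. Appendix A obliges trained personnel to elicit events in either arm, section 11.13.1 says the named events will be collected, section 9.1 requires training in safety reporting, and the adverse-event form, SOPs and intervention manual are not in the documents and may hold specific items. For a behavioral pilot, an open question with trained follow-up can also be defended as a normal choice.

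Much of this stands. A reader might infer that infant and custody harms are recorded only if the mother volunteers them. The documents do not support that: elicitation is required, NAS and pediatric visits come from records, and the other coverage in Step 1 does not wait on her. A reader might also infer that no instrument asks about custody. Section 8.0 gives instrument names and not their items, so the most that can be said is that no row is named for it.

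What the reply does not supply is a question or a scheduled check. The duty to elicit comes with no wording beyond that in 8.2.1. A form described as capturing reportable events shows where a known event is entered, not that anyone asks about it. If the unseen forms do contain prompts, citing them in 8.2.1 would settle the matter.

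**Conclusion.** The concern holds in a limited form. As documented, finding child protective services involvement, child removal and birth defects as adverse events depends largely on a non-specific question and unscripted elicitation. Pre-term birth shares the problem to a lesser degree. The remaining named events have at least a partial route. Because navigation participants have many more occasions to disclose, the data reaching the benefit-risk review may be uneven between arms.

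The size cannot be given in events. The documents state neither how often these events occur nor what share an open question would find, and any count would be invented. A reader might go further and conclude that a planned safety comparison between arms is biased. Section 10.3 plans no such comparison, and the DSMB provisions do not say that listings are split by arm. The supportable statement is about completeness and evenness of the data under review.

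This rests on two assumptions: that the unseen forms and SOPs add no specific prompts, and that longer contact about family and newborn matters brings out more such events. Confidence is moderate. The change is worth making because it is cheap and aligns what is asked with what Appendix A promises.

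**What to change.** In section 8.2.1, keep the open question and state who asks it in each arm, consistently with Appendix A. Add a short yes/no list, read verbatim at the three follow-up assessments in both arms and covering the time since the last assessment:

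- at all three: child protective services contact, child removal, maternal hospital stay;
- at the two postnatal assessments: infant death, birth defect, infant hospital stay.

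The hospital-stay items reflect the hospitalization criterion for seriousness in Appendix A. Relapse needs no new item. Take pre-term birth and birth defects also from the delivery record, using the access under section 7.2, and confirm that this access covers the infant's chart and deliveries elsewhere. In DSMB reports, flag events learned only in navigator sessions, so that the board can see which events came from a source open to one arm only. The questions need not reveal allocation, so the blinded assessor in section 7.9.2 can read them.

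The cost is an estimated two minutes per assessment (3 × 2 = 6 minutes per woman over follow-up), one REDCap form, protocol wording, and more events to process under the existing reporting rules. A direct question will not remove reluctance to disclose custody events, so capture should become more complete and more even, but not perfect.

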### **8.2.2 Suicidal Behavior Evaluation**

Within the Patient Health Questionnaire is embedded a validated single item suicide screening tool. This item is assessed at each visit. If the participant screens positive for depression, the navigator will ensure the participant contacts the Resolve Crisis Center to arrange for follow up ([name]) within the University of Pittsburgh or the Crisis and Interventional and Hospital Diversion Crisis Line within the University of Utah ([name]). If the participant screens positive for suicidality, the navigator will immediately follow the study Suicide Management Plan (see REDCap form). Similarly, if the participant appears to be intoxicated or reports experiencing symptoms of opioid withdrawal, the navigator will immediately notify the site study physician who can further assess and direct steps for possible additional care depending on participant need.

## **9.0 TRAINING REQUIREMENTS**

### **9.1 Overall**

A Training Plan will be developed to incorporate general training, study-specific training, mechanisms for competency assessment as well as a detailed description of training, supervision, and fidelity monitoring procedures. The Investigative Team is responsible for the development of a comprehensive Training Plan, instructional material, and delivery of the training.

Training will include Human Subjects Protection (HSP) and Good Clinical Practice (GCP) as well as protocol-specific training on assessments, medication management for pharmacological studies, study interventions, safety and safety event reporting, study visits and procedures, data management, quality assurance, laboratory procedures, etc. The University of Utah site is primarily responsible for development and delivery of study-specific training related to the study intervention(s) and procedures. The University of Utah site also is responsible for training related to data management, the electronic data capture system, and good data management practices.

Study staff is required to complete institutionally required training per their research site, Institutional Review Board(s), and authorities with regulatory oversight. Tracking of training completion for individual staff as prescribed for assigned study role(s) will be documented, endorsed by the site Principal Investigator and the project coordinator. As changes occur in the prescribed training, the Training Plan and training documentation tracking forms will be amended to reflect these adjustments.

## 10.0 STATISTICAL DESIGN AND ANALYSES

### 10.1 General Design

This study design for this project is a small scale, multisite, phase 2, single blinded, randomized clinical trial. Randomization will be stratified by hospital site and performed in blocks of 6 to ensure an even distribution of Magee and University of Utah participants in PN and standard care groups.

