### **5.2 Participant Exclusion Criteria**

All women meeting any of the exclusion criteria at baseline will be excluded from study participation:

- Experienced a psychotic or a manic episode in the last 30 days documented in their medical record or self report
- Beyond the 32nd week of gestation
- Cannot provide collateral contact information of 2 persons
- Cannot provide a reliable phone number
- Plan to move from the area within study recruitment to 6 months after their delivery
- Inability or unwillingness of subject to give written informed consent.
- Other factors that would cause harm or increased risk to the participant or close contacts, or preclude the participant's full adherence with or completion of the study
- Has been on buprenorphine or methadone for  $>6$  weeks.

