## **6.0 SITES**

### **6.1 Number of Sites and Participant Flow**

Two sites will be used for participant recruitment in this study. A total of 122 women will be recruited for participation in this study. We anticipate an even distribution of 61 women recruited at each site. For the 61 women recruited and randomized to the PN condition, we expect approximately 30 will be recruited at the University of Utah and 31 at the University of Pittsburgh. Based on estimates of a recruitment window of 15 months and active intervention delivery across 24 months, we will recruit approximately 5 patients per month between both sites. In terms of monthly patient caseload during the 6 busiest months of the study, each site will have approximately 9 to 12 active (pre and postnatal) participants at one time.

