#### 7.4 Randomization

Following the baseline assessment, participants will be randomized on a 1:1 basis to PN or standard care (i.e., short-term case management + referral). The study statistician will create a randomization list to assign patients to treatment or control conditions. The statistician will also review the randomization data on a regular basis to ensure that the scheme is being implemented according to plan. If a participant drops out of the study at any point after randomization, the randomization slot will not be re-allocated to a new patient due to the intent-to-treat nature of the study.

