### **7.9.2 Maintenance of the Blind**

The individuals blinded to the study condition will be those conducting the study assessments. The baseline assessment will be blinded given that the randomization will not be revealed until after the assessment is completed. The follow up assessments will be conducted by a blinded research assistant.

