### **7.9.3 Breaking the Blind**

As the research assistant is the only blinded party, there is no scenario in which the blind will need to be broken. Investigators providing clinical management and decision-making are informed of each participants randomization result.

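### One fixed block size of 6 within each of two sites leaves about a quarter of assignments deducible by anyone who knows the block size and the earlier allocations

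*Combined protocol and SAP*

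**What the plan says.** Section 10.1 sets the method: "Randomization will be stratified by hospital site and performed in blocks of 6". Section 7.4 gives the ratio, "participants will be randomized on a 1:1 basis to PN or standard care", so each block holds three PN and three standard-care places. No second or random block size appears anywhere.

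On concealment, section 7.4 says "The study statistician will create a randomization list to assign patients to treatment or control conditions", and section 7.9.2 says "the randomization will not be revealed until after the assessment is completed". Section 7.9.3 limits the blind ("As the research assistant is the only blinded party") and adds: "Investigators providing clinical management and decision-making are informed of each participants randomization result".

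Neither section 7.4 nor section 10.1 describes central or web-based assignment or sealed envelopes, or keeps the block size or past allocations from those who screen and consent. Sections 7.1 and 7.1.1 refer to an SOP on screening, consent and blinding whose text is not included.

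**The concern.** With a known fixed block, once three women in one arm have appeared, every remaining place in that block belongs to the other arm. The prediction comes from past allocations, so neither a list held by the statistician nor late release of the current entry prevents it.

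If someone who influences entry could make that prediction, there is room to act on it. Study staff find women in medical records, send letters and make follow-up calls (section 5.3). Section 5.2 contains a judgement-based exclusion for factors that would "preclude the participant's full adherence with or completion of the study". At 61 women per site over 15 months, entries arrive at about four a month (61/15 = 4.1), which is slow enough to tally.

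The primary outcomes are treatment linkage and retention, abstinence, MAT adherence and use of psychosocial services. Motivation at entry bears on all of them. If it differed between arms, the preliminary signal meant to support a fully powered trial would be biased.

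**Working it through.** **Inputs.** Block size 6 and two site strata (section 10.1); 1:1 ratio (section 7.4); 61 women per site (section 6.1: "We anticipate an even distribution of 61 women recruited at each site"); total 122 (section 10.2.2). The documents give no predictability figure. The one stated figure used here is the total, which reproduces: (141 + 58) × 15/12 × 0.70 × 0.70 = 121.9, or 122.

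**Step 1: fully determined assignments in one block.** There are C(6,3) = 20 equally likely orderings. An assignment is determined when one arm has already used its three places.
- Third place of an arm filled at position 3: 2 orderings, 3 determined, probability 2/20 = 0.1.
- Filled at position 4: 2 × C(3,2) = 6 orderings, 2 determined, probability 0.3.
- Filled at position 5: 2 × C(4,2) = 12 orderings, 1 determined, probability 0.6.

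The expected number is 3 × 0.1 + 2 × 0.3 + 1 × 0.6 = 1.5 of 6, or 25%. The closed form for block size 2m agrees: 2m/(m+1) = 6/4 = 1.5. At least one assignment per block is always determined.

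**Step 2: the whole trial.** 61 women make 10 full blocks plus one woman, whose assignment cannot be determined. Per site: 10 × 1.5 = 15 of 61. Both sites: 30 of 122 (24.6%). The minimum is 20 × 1 = 20 of 122 (16.4%).

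The site split hardly matters. The yearly counts in section 10.2.2 imply about 86 and 36 women (141 × 1.25 × 0.49 = 86.4; 58 × 1.25 × 0.49 = 35.5). That is 14 full blocks plus two women, and 6 full blocks, so 20 × 1.5 = 30 of 122 again.

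**Step 3: best-guess rate.** Always guessing the arm with more places left is right 4.1 times in 6 (68.3%). Over 61 women it is (10 × 4.1 + 0.5)/61 = 68.0%, against 50% with no information.

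**Step 4: undisclosed, randomly varying sizes.** Lists of 61 per site were simulated (4,000 per set, sizes equally likely). The observer knows the set of sizes and all earlier allocations, but not the size of the current block. The sets are assumptions for illustration. The largest imbalance is half the largest block.

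| Block sizes | Fully determined | Best guess right | Largest within-site imbalance |
|---|---|---|---|
| 6 (plan) | 24.6% | 68.0% | 3 |
| 4, 6 | 5.6% | 68.9% | 3 |
| 2, 4, 6 | 4.1% | 69.8% | 3 |
| 4, 6, 8 | 2.2% | 67.6% | 4 |
| 6, 8, 10 | 1.7% | 66.0% | 5 |

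For 4, 6 and 8, separate simulations gave 2.2% to 2.5%, or about 3 of 122 (0.022 × 122 = 2.7; 0.025 × 122 = 3.1). Certainty largely disappears; moderate predictability does not.

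**The case against.** The strongest reply is that a route to bias is not documented.

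- **Who knows the allocations.** Section 7.9.3 names only investigators giving clinical management as informed of each result. A reader might infer that navigators, coordinators and everyone else at a site see every allocation. Some see part of it through their work: section 7.5 has the coordinator and investigators checking PN recordings, and section 7.10 has coordinators or research assistants paying for navigator sessions. Full knowledge of the sequence by any of them remains an inference.
- **Who enrols.** Sections 7.1 and 7.1.1 say only that staff screen and consent. If the blinded research assistant did all of it and stayed blind, the 25% would not apply. The unseen SOP may settle this.
- **Existing safeguards.** The statistician reviews the randomization data regularly (section 7.4). Both sites log approaches, ineligibility and refusals with reasons (section 5.3). Some women enter through hospital referral, a research registry or flyers. The gestational limit and the limit on prior buprenorphine or methadone treatment restrict how long anyone could be held back. These make steering harder and leave a partial trail, but do not stop prediction.
- **Purpose and analysis.** Section 10.2.2 says definitive testing is not the aim. The models in section 10.3 can include baseline predictors, so it would be too strong to say that analysis can do nothing. They can adjust for measured imbalance, but not for unmeasured motivation.
- **Size of the gain.** The best-guess rate barely moves under varying blocks, so 68% is not a fault peculiar to the fixed size.

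These points limit the claim to a vulnerability and the benefit to removing near-certainty. They do not supply a reason to keep one disclosed block size.

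**Conclusion.** The concern holds as a design weakness that is cheap to reduce. An expected 25% of assignments per block, about 30 of 122 overall and at least 20, are fully determined for a person who knows the block size and every earlier allocation at that site in order. The figure is an expectation for such an observer and assumes the list is built as section 10.1 states.

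A reader might go further and infer that enrolling staff did know a quarter of the assignments, or that women were steered. The documents do not support that. They do not say who enrols, whether those staff hold the block size or the allocation history, or what the SOP requires. Nor does a block size printed in the protocol show that recruiters used it.

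**What to change.** For the rest of recruitment, starting at the next block boundary at each site, generate the list with randomly varying block sizes within site, for example 4, 6 and 8. In section 10.1, replace the stated block size with: *randomly permuted blocks of varying size, held by the statistician*. Keep the sizes out of all site documents. State in section 7.4 who enrols and how past allocations are kept from them, or bring in the relevant steps from the SOP. Release after the baseline assessment is already planned and needs no change.

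The cost is regenerating the unused part of the list and editing a few sentences. With sizes 4, 6 and 8, the largest within-site imbalance rises from 3 to 4 women if the switch is made at a block boundary. Made mid-block, a leftover imbalance of up to 3 could add to 4, giving up to 7. Sizes 4 and 6 would keep the maximum at 3, with about 5.6% of assignments still determined. Varying sizes leave the guess rate near 68%, so restricting enrolling staff's access to past allocations is the needed complement.
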